7.2.6.8. Weight and Height

Body weight will be recorded at the time points shown in the Schedule of Assessments ([Table 2](#) and [Table 4](#)). Body weight, with the patient wearing light clothing and the shoes and jacket or coat removed, will be measured and recorded in kilograms.

Body height will be measured and recorded, in centimeters, at Screening only.

7.2.6.9. Electrocardiogram

A 12-lead ECG will be taken at the time points shown in the Schedule of Assessments ([Table 2](#) and [Table 4](#)). The ECG should be performed after the patient has rested for at least 5 minutes in a supine position. When scheduled at the same time point as vital sign measurements or a blood sample collection, the ECG should be performed first.

The ECG measurements will include heart rate, PR interval, QT interval, RR interval, QRS complex, and rhythm. It is preferable that the machine used has a capacity to calculate the standard intervals automatically. Corrections to QT interval should be done by both QTcF and QTcB, if possible.

The Investigator or qualified designee will review and indicate if the ECG is normal or abnormal, and whether clinically significant. Any medically significant changes from the screening ECG will be recorded as an AE.

7.2.6.10. Clinical Laboratory Tests

Clinical laboratory tests for safety (hematology, serum chemistries, urinalyses, coagulation tests, serum pregnancy) and other tests during scheduled visits will be performed at a central laboratory. Urine pregnancy tests and erythrocyte sedimentation rate (ESR) will be performed locally using an approved test; TB testing may be performed locally or centrally using a licensed test.

Clinical laboratory results the Investigator deems clinically significantly abnormal should be repeated ideally within 48 to 72 hours from when the result became available. Guidance for laboratory values that could be considered clinically significantly abnormal is provided in [Appendix B](#). Certain clinically significantly abnormal laboratory values may also influence continued dosing as per [Section 6.1.1](#).

Unscheduled or additional laboratory samples may be collected and analyzed by local laboratories if immediate results are necessary for management of TEAEs or dosing determination. Unless otherwise noted, when scheduled simultaneously with a dosing visit, samples for laboratory evaluations should be collected prior to administration of the study drug.

Detailed instructions for sample collection, processing, storage and shipment will be provided in the Laboratory Manual.

7.2.6.11. Hematology and Erythrocyte Sedimentation Rate

Samples for hematology and ESR will be collected, and testing will be performed at the time points shown in the Schedule of Assessments ([Table 2](#) and [Table 4](#)). Hematology tests to be performed are presented in [Table 6](#).

Table 6 Hematology Tests

Hematology Tests

• Hemoglobin• Hematocrit• WBC count (total and differential)• Red blood cell (RBC) count• Platelet count• Mean corpuscular volume (MCV)• Mean corpuscular hemoglobin (MCH)• MCH concentration (MCHC)

The ESR will be measured by the local laboratory, and the value entered into the eCRF.

7.2.6.12. Clinical Chemistry, C-Reactive Protein, and Aldolase

Samples for clinical chemistry will be collected for patients in a nonfasting state, and testing will be performed at the time points shown in the Schedule of Assessments ([Table 2](#) and [Table 4](#)). Clinical chemistry tests to be performed are presented in [Table 7](#).

Table 7 Clinical Chemistry, Aldolase, and C-Reactive Protein Tests

Serum Chemistry Tests (Non-Fasting)	

• Creatinine• Creatine kinase (CK)• Urea (or blood urea nitrogen [BUN])• Aspartate aminotransferase (AST)• Alanine aminotransferase (ALT)• Gamma glutamyltransferase (GGT)• Alkaline phosphatase• Lactate dehydrogenase (LDH)• Total bilirubin• Albumin• Total protein	
• Sodium• Potassium• Chloride• Glucose• Uric acid• Total cholesterol• Magnesium (Mg)• Calcium• Phosphorus• C-reactive protein (CRP)• Aldolase

Patients will have estimated glomerular filtration rate (eGFR) calculated based on CKD-EPI formula:

$$\text{eGFR} = 141 \times \min(S_{\text{cr}}/\kappa, 1)^{\alpha} \times \max(S_{\text{cr}}/\kappa, 1)^{-1.209} \times 0.993^{\text{Age}} \times 1.018 \text{ [if female]} \times 1.159 \text{ [if black]}$$

Where:

- S_{cr} is serum creatinine in mg/dL
- κ is 0.7 for females and 0.9 for males
- α is -0.329 for females and -0.411 for males
- min indicates the minimum of S_{cr}/κ or 1
- max indicates the maximum of S_{cr}/κ or 1.

7.2.6.13. Urinalysis

Samples for urinalysis will be collected and testing will be performed at the time points shown in the Schedule of Assessments ([Table 2](#) and [Table 4](#)). Urinalysis will include: color, appearance, specific gravity, pH, protein, glucose, ketones, bilirubin, blood, urobilinogen, nitrite, leukocyte esterase with reflex testing for microscopic parameters.

7.2.6.14. Immunoglobulins

Samples for immunoglobulins will be collected and testing will be performed at the time points shown in the Schedule of Assessments ([Table 2](#) and [Table 4](#)). Quantitative immunoglobulins measured will include IgG, IgM, and IgA.

7.2.6.15. CD19 Count

At Screening, a CD19 count is required to be performed only for those patients being evaluated for eligibility who had their last dose of rituximab ≥ 24 and < 48 weeks before Screening.

7.2.7. Pharmacokinetic Assessments

Blood samples will be collected as outlined in the Schedule of Assessments ([Table 2](#) and [Table 4](#)). All patients will have blood samples collected at predose and at 0.5 and 4 hours postdose. In addition, patients will be randomly assigned via RTSM to Cohort A (0.25 hour postdose PK sample), Cohort B (1 hour postdose PK sample), or Cohort C (2 hour postdose PK sample). Samples will be used to measure the plasma concentration of KZR-616 and its metabolite KZR-59587 (area under the time-concentration curve [AUC], maximum concentration [C_{max}], time to maximum plasma concentration [T_{max}]), and other PK calculations). At the visits and times specified, blood samples of approximately 4 mL will be collected. Additional information regarding sample collection and handling are outlined in the Laboratory Manual.

Samples collected to measure investigational product concentration and metabolism and/or protein binding will be retained for as long as legally permitted in the country of origin or until Sponsor decision to destroy.

7.2.8. Pharmacodynamic Assessments

The extent of proteasome activity in whole blood and isolated PBMCs will be assessed in blood samples collected as outlined in the Schedule of Assessments ([Table 2](#) and [Table 4](#)). Proteasome CT-L peptidase activity will be measured by a cleavable fluorogenic substrate enzymatic activity assay. KZR-616 occupancy of individual subunits of the proteasome in whole blood and PBMCs will be measured by the proteasome constitutive/immunoproteasome subunit enzyme-linked immunosorbent assay (ELISA) (ProCISE), a subunit-specific proteasome active site ELISA.

Additional information regarding sample collection and handling are outlined in the Laboratory Manual.

7.2.9. Exploratory Biomarkers

7.2.9.1. Cytokines, Proteomics, and Leukocyte Subsets

Blood samples will be collected at the times shown in the Schedule of Assessments ([Table 2](#) and [Table 4](#)) for the measurement of cytokines by ELISA including IFN α , IFN β , IFN γ , IL-2, IL-6, IL-12, IL-17A, IL-21, IL-23, CXCL10, BLyS, TNF α , TGF β ; and to profile immune cells by flow cytometry including B cell subgroups (naïve, activated, memory), plasma cell subgroups (long, short-lived), T cell subgroups (CD4 [Th1, Th17, all, naïve, activated], CD8 [memory], Treg). Immune cell profiling may also be performed by immune cell subset identification by deoxyribonucleic acid (DNA) methylation polymerase chain reaction methodology. Additional information regarding sample collection and handling are outlined in the Laboratory Manual.

7.2.9.2. Autoantibodies

Blood samples will be collected at the times shown in the Schedule of Assessments ([Table 2](#) and [Table 4](#)) for the measurement of autoantibodies. Autoantibodies that may be assessed

include the following: myositis autoantibodies: anti-Jo-1, anti-PL-7, anti-PL12, anti-EJ, anti-OJ, anti-SRP, anti-Mi-2 α , anti-Mi-2 β , anti-MDA-5, anti-TIF-1 γ , anti-NXP-2, anti-HMGCR; other autoantibodies: anti-PM-Scl, anti-U1RNP, anti-SSA, anti-SSB, anti-Ku, anti-SAE, anticentromere, and antinuclear.

Additional information regarding sample collection and handling are outlined in the Laboratory Manual.

7.2.9.3. Pharmacogenomics/Gene Expression

Gene expression (ribonucleic acid [RNA]) profiling and DNA genotyping and methylation status may be assessed in blood samples. A whole blood sample will be collected for pharmacogenomic analysis for storage and analysis at a later date as specified in the Schedule of Assessments ([Table 2](#) and [Table 4](#)) and to the extent permitted by the national and/or local laws and regulations.

Samples will be used to conduct retrospective disease or population genetic research as a separate analysis not included in this study. Samples may be used to investigate variable response to KZR-616 and to investigate genetic or epigenetic variants thought to play a role in the diseases under investigation in this study. Assessment of variable response may include evaluation of AEs or differences in efficacy. The results may be reported in the separate report.

Additional information regarding sample collection and handling are outlined in the Laboratory Manual.

7.2.9.4. Biopsy

Biopsies will be collected from a subset of enrolled patients; skin biopsies will be performed only for selected patients with DM, and muscle biopsies will be performed for selected patients with PM or DM. For selected patients, biopsies will be collected from skin and/or muscle at the time points shown in the Schedule of Assessments ([Table 2](#) and [Table 4](#)). The tissue samples may be used for exploratory investigations of treatment-related changes and regulation of inflammatory pathways.

Additional information regarding sample collection and handling are outlined in the Laboratory Manual.

8. STUDY DISCONTINUATION

The Investigator must make every reasonable effort to keep each patient on study for the whole duration of the study, including through the SFU, lost to follow-up, consent withdrawal, or End of Study, whichever occurs first.

8.1. Individual and Study Stopping Rules for Safety

8.1.1. Study Stopping Rules

If any of the following events occur, the accumulated safety data will be reviewed by the DMC.

- Death in any patient, unless the cause of death is due to obvious alternative etiology
- Any unexpected or life-threatening SAE, unless due to obvious alternative etiology
- Any event of TMA, thrombotic thrombocytopenic purpura (TTP), or hemolytic uremic syndrome (HUS)
- Three or more of the same Grade 3 or higher AE (judged by the Investigator, Medical Monitor, or Sponsor's representative), including ISRs, unless due to obvious alternative etiology
- Any event which, in the opinion of the Investigator, Medical Monitor, DMC, or Sponsor, contraindicates further dosing of additional patients.

Based on the review, the DMC will have the ability to recommend the study be continued as is, continued with modification, or discontinued. Modifications could include eg, implementation of additional monitoring measures or a dose reduction of KZR-616.

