6.1.1. Dosing Criteria

All patients must meet the following criteria before each dose:

- Absolute neutrophil count $\geq 1.0 \times 10^9/L$ as of the most recent laboratory testing
- Hemoglobin $\geq 8.0 \text{ g/dL}$ and $\leq 16.5 \text{ g/dL}$ as of the most recent laboratory testing
- Platelets $\geq 50,000/\text{mm}^3$ and $\leq 1,000,000/\text{mm}^3$ as of the most recent laboratory testing
- Serum ALT or AST $\leq 3 \times \text{ULN}$ and total bilirubin $< 2 \times \text{ULN}$
- Non-ISR AEs \leq Grade 2.

Dosing should be held until the AE improves to \leq Grade 2 or the laboratory abnormality is within the range to allow dosing (please see [Section 6.1.4.2](#) regarding missed doses), unless there is Medical Monitor or Sponsor approval to permit dosing. Any laboratories with values that preclude dosing should be repeated as soon as possible (as per [Section 7.2.6.10](#)).

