6.1.3. Monitoring of Dose Administration

Systemic injection reactions have been observed with KZR-616 and other proteasome inhibitors; the following guidance is based on these known experiences^{45,23} and may be modified as clinical experience with KZR-616 evolves and matures.

In KZR-616-001, 4 of 12 healthy volunteer subjects who received 60 mg KZR-616 SC experienced AEs with the preferred term of adverse drug reaction; consisting of hypotension, tachycardia, nausea, vomiting, rigors, and/or chills, associated with an acute phase-like response, including leukocytosis and elevated C-reactive protein (CRP), which occurred approximately 8 to 12 hours after dosing. These events are similar to the infusion-related reactions observed with the currently marketed proteasome inhibitor carfilzomib, which generally occur in the first cycle of dosing.

Systemic injection reactions with other proteasome inhibitors include a number of signs and symptoms, including fever, chills, myalgia, facial swelling or flushing, vomiting, weakness, hypotension, chest tightness, and shortness of breath, as well as abnormalities in laboratory values (eg, creatinine, transaminases). However, the relative roles of the immunoproteasome versus constitutive proteasomes to these specific events are not known. The individual signs/symptoms of systemic injection reactions must be reported as AESIs within 24 hours using the AE electronic case report form (eCRF) (refer to [Section 9.5.1](#)).

With other proteasome inhibitors, prophylactic measures such as pre-dose hydration and low-dose dexamethasone (4 mg) reduce the incidence and severity of infusion-related reactions. Therefore, upon the development of signs and/or symptoms suggestive of a systemic drug reaction, the following interventions are suggested:

- Supportive measures, including the administration of oral and/or IV fluids, antiemetics, acetaminophen, antihistamines and/or systemic corticosteroids (eg, prednisone 25 mg – equivalent to 4 mg of dexamethasone)
- Collection of serum and/or plasma samples for analysis of potentially elevated levels of eg, cytokines, histamines
- For patients who develop signs and/or symptoms that may be consistent with a cardiac etiology (eg, hypo- or hypertension, tachycardia, arrhythmia, or abnormal cardiac enzymes), the following should be obtained to rule out cardiac toxicity which has been described with proteasome inhibitors:

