8.1.2. Individual Patient Stopping Rules

If any of the following events occur in an individual patient, administration of study drug to the patient should be interrupted until a review of the accumulated safety data is undertaken by the DMC.

- Any event that fulfills criteria for a Study Stopping Rule (per [Section 8.1.1](#)), unless due to obvious alternative etiology
- Any event that, in the opinion of the Investigator, Medical Monitor, DMC, or Sponsor, contraindicates further dosing

After such a review, the DMC may recommend the patient resume dosing, including consideration for any prophylactic interventions (eg, as per [Section 6.1.3](#)); reduce their dose (as per [Section 6.1.4.1](#)), or discontinue dosing.

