9.1.2. Assessment of Severity

Severity of AEs will be graded according to National Cancer Institute Common Terminology Criteria for Adverse Events (NCI-CTCAE) Version 4.03. If there is a change in severity of an AE, it must be recorded as a separate event.

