9.1.6. Documentation and Reporting of Adverse Events

Adverse events (including SAEs) should be reported and documented in accordance with the procedures outlined below. All AEs occurring during the study must be documented on the relevant eCRF pages. The following data should be documented for each AE:

- Diagnosed or description of the symptom if diagnosis is not established
- Classification of 'serious' or 'not serious'

- Classification as AESI (yes or no)
- Severity
- Date of first occurrence and date of resolution (if applicable)
- Action taken with study drug
- Causal relationship with study drug
- Outcome of event (unknown, recovered, not yet recovered, recovered with sequelae, death [with date and cause reported]).

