9.5.1. Systemic Injection Reactions

Systemic injection reactions have been observed with KZR-616 and other proteasome inhibitors and are considered AESIs.

Systemic injection reactions have included a number of signs and symptoms including fever, chills, myalgia, facial swelling or flushing, vomiting, weakness, hypotension, chest tightness, and shortness of breath, as well as abnormalities in laboratory values (eg, creatinine, transaminases). The relative roles of the immunoproteasome versus constitutive proteasomes to these specific events are not known. Therefore, terms such as eg, the NCI-CTCAE or Medical Dictionary for Regulatory Activities (MedDRA) terms of ‘injection related reaction,’ ‘cytokine release syndrome,’ ‘systemic immune activation,’ ‘drug hypersensitivity,’ ‘hypersensitivity reaction,’ or ‘allergic reaction’ should not be used. Instead, each sign or symptom should be recorded as an individual AE with its own level of severity, even if multiple signs or symptoms occur.

Management of systemic injection reactions is described in [Section 6.1.3](#).

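### Section 8.1.1 counts repeats of the same Grade 3+ AE, but Section 9.5.1 records systemic injection reactions sign by sign, and nothing regroups the signs for the count

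*Combined protocol and SAP*

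**What the plan says.** Section 8.1.1 lists five events that lead to DMC review. Four can be met by a single event. The fourth bullet is the only one with a count: "Three or more of the same Grade 3 or higher AE". A parenthesis adds that the Investigator, Medical Monitor or sponsor's representative judges this. The bullet includes ISRs and excepts events with an obvious other cause. The list of abbreviations defines ISR as injection site reaction, so systemic reactions are not named.

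Section 9.5.1 makes systemic injection reactions AESIs, rules out umbrella terms such as cytokine release syndrome, and asks that "each sign or symptom should be recorded as an individual AE with its own level of severity". The clinical signs it lists are "fever, chills, myalgia, facial swelling or flushing, vomiting, weakness, hypotension, chest tightness, and shortness of breath", with laboratory abnormalities in addition. Section 6.1.3 describes the reactions seen in healthy volunteers at 60 mg as "hypotension, tachycardia, nausea, vomiting, rigors, and/or chills".

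Two other sections set the consequence. Section 8.1.2 interrupts a patient's dosing pending DMC review for "Any event that fulfills criteria for a Study Stopping Rule", or on opinion. Section 6.1.1, which applies to any non-ISR AE above Grade 2, says "Dosing should be held until the AE improves to" Grade 2 or lower, unless the Medical Monitor or sponsor approves dosing.

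**The concern.** Section 8.1.1 does not say what makes two AEs the same, and the recording rule spreads one clinical entity over many terms. TMA, the other AESI, has its own bullet in 8.1.1; systemic injection reactions have none.

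At stake is whether a cluster of severe reactions reaches the DMC by rule or only because someone notices it. A non-serious Grade 3 reaction, or one that is serious but expected and not life-threatening, does not meet the SAE bullet. If the count is not met and nobody uses a discretionary route, only the hold in 6.1.1 applies. In the one recurrence described in Section 1.3, symptoms had resolved by about 24 hours. With weekly dosing, a hold that ends that soon may delay nothing, and the third patient could be dosed again without a DMC review having been called.

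**Working it through.** The plan states no operating characteristic for this rule, so there is no figure to reproduce. The check is first one of wording, then an illustration on stated assumptions.

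**1. The two rules side by side.** Suppose patient 1 has Grade 3 hypotension, patient 2 Grade 3 vomiting and patient 3 Grade 3 chills. Under 9.5.1 these are three different AEs. The counts are 1, 1 and 1, so the largest is 1 and the threshold of 3 is not met. Grouped as reactions, the count is 3.

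**2. Exactly three reactors.** Assume each has *m* Grade 3+ signs, drawn independently and with equal weight from *k*, and no recurrence. The count is met if some sign is common to all three.

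- *m* = 1: *k* × (1/*k*)³ = 1/*k*². This gives 1/36 = 2.8% for *k* = 6 and 1/81 = 1.2% for *k* = 9.
- *m* = 2: *k* × (2/*k*)³ − C(*k*,2) × [1/C(*k*,2)]³ = 8/*k*² − 1/C(*k*,2)². The subtracted term corrects for all three sharing the same pair.
  - *k* = 4 (nausea, vomiting, dizziness and chills, Section 1.3): 0.500 − 1/36 = 47%.
  - *k* = 6 (list in 6.1.3): 0.2222 − 1/225 = 22%.
  - *k* = 9 (list in 9.5.1): 0.0988 − 1/1296 = 9.8%.
- *m* = 3, *k* = 4: each patient lacks one sign of four, so three patients lack at most three and one sign is always shared: 100%.

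Grouped by patient, the count is met in 100% in every case.

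**3. All 24 patients.** Let *p* be the share with a Grade 3+ reaction. The documents give no value for 30 mg then 45 mg, so a range is shown. Grouped by patient, the chance is P(X ≥ 3) with X ~ Bin(24, *p*). For *p* = 10%: 1 − (0.0798 + 0.2127 + 0.2718) = 0.436.

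For the same-sign count, the chance is the sum over *n* of C(24,*n*) *p*ⁿ(1−*p*)²⁴⁻ⁿ × *q*ₙ. Here *q*ₙ is the exact chance that some sign reaches three records among *n* reactors, with two signs each. In the last two columns records are counted, and each reactor has a 50% chance of one recurrence with the same signs, which gives two records per sign. Two reactors can then be enough.

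| *p* | Grouped, by patient | Same sign, 6 signs, no recurrence | Same sign, 9 signs, no recurrence | Same sign, by record, 6 signs, half recur | Same sign, by record, 9 signs, half recur |
|---|---|---|---|---|---|
| 2% | 1.2% | 0.3% | 0.2% | 4.2% | 3.0% |
| 5% | 12% | 3.8% | 2.0% | 20% | 16% |
| 10% | 44% | 20% | 12% | 52% | 43% |
| 20% | 89% | 67% | 50% | 89% | 84% |

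**4. What the table shows.** If patients are counted, or reactions do not recur, the same-sign rule is the less sensitive: at *p* = 10%, 20% or 12% against 44%. If records are counted and half of reactors recur, the rule as written can be the more sensitive: with six signs, 52% against 44% at *p* = 10%. A grouped patient count should therefore be added to the existing bullet and should not replace it.

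**The case against.** The strongest reply is that the fourth bullet is not mechanical. The *judged by* parenthesis can be read to cover sameness as well as grade and cause, and 9.5.1 restricts the terms used for recording, not how a judge may view them. Section 1.5 puts a participating Investigator, a Medical Monitor and a sponsor representative on the DMC. These are the roles that judge the count, and the DMC may itself use the opinion-based bullet. Reaction signs are entered as AESIs within 24 hours. A cluster goes unreviewed only if three severe reactions among 24 patients prompt none of these people to act. The DMC charter, which might group reactions, was not supplied. All of this stands. It limits the consequence but does not supply a grouping rule.

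The rates are also uncertain. At 60 mg, all five lupus patients had Grade 1 or 2 events. Two healthy-volunteer SAEs of adverse drug reaction are reported without a grade (Section 1.5). Signs that tend to occur together narrow the gap, as the four-sign case shows.

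Three stronger readings are tempting and not supported.

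- A reader might infer that DMC review of such a cluster is blocked. It is not: the discretionary routes remain open, and one unexpected or life-threatening SAE is enough.
- A reader might infer that the existing bullet should count patients throughout. That could weaken it, for reactions (step 4) and for other AEs: if records are counted, three Grade 3 injection site reactions in one or two patients call a review now and would not then.
- A reader might infer from Section 9.1.2 ("If there is a change in severity of an AE, it must be recorded as a separate event") that one continuing AE graded 3, 4 and 3 counts as three. That section is a recording instruction, and 8.1.1 does not make records the unit. Such a reading would in any case lead only to an extra review.

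**Conclusion.** The mismatch is in the text. Followed literally, 8.1.1 and 9.5.1 together leave three Grade 3+ systemic injection reactions with no shared sign outside the only numerical trigger, and review then rests on judgement, opinion or general oversight.

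The practical size is unknown and may be close to zero at the doses used. The percentages in the working describe how the rule behaves if severe reactions occur. They rest on assumed rates, equally likely and independent signs, and mostly two signs per patient; they are not forecasts for this trial. The bullet calls a review and does not stop the study. This is a low-cost safety improvement, made worthwhile because the protocol itself treats these reactions as of special interest.

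**What to change.** Keep the fourth bullet of 8.1.1 as it stands and add one bullet:

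> Three or more patients with a Grade 3 or higher systemic injection reaction (any AESI-flagged sign other than TMA/TTP/HUS, each patient counted once), unless due to obvious alternative etiology.

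Because 8.1.2 refers back to the 8.1.1 criteria, it picks up the new trigger without further editing. Symptom-level recording in 9.5.1 has a stated reason and stays. No clause on grade changes is needed.

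The AESI classification and the severity grade are already collected for every AE under Section 9.1.6, so there is no new data item, visit or table. Adding a trigger cannot make the existing rule less sensitive. The downside is an occasional extra DMC review.
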